5.3.3.1 Primary Variable

The primary efficacy endpoint is the percentage of subjects with SVR₁₂ (HCV RNA < LLOQ 12 weeks after the last dose of study drug), both overall and according to treatment in the previous study.

5.3.3.2 Secondary Variable

The secondary efficacy endpoints are the percentage of subjects with SVR₂₄ (HCV RNA < LLOQ 24 weeks after the last dose of study drug) and the percentage of subjects with eRVR (HCV RNA < LLOQ at TI Weeks 4 through 12). The endpoints will be examined for the overall treated group and according to the previous treatment as appropriate.

5.3.3.3 Resistance Variables

The following resistance analyses will be performed for subjects who do not achieve SVR: the variants at each amino acid position identified by population and/or clonal nucleotide sequencing (1) at baseline will be compared to the appropriate prototypic reference sequence, and (2) at available post-baseline time points will be compared to baseline and the appropriate prototypic reference sequences.

5.3.4 Safety Variables

The following safety evaluations will be performed during the study: adverse event monitoring and vital signs, physical examination, ECG, and laboratory tests assessments.

5.3.5 Pharmacokinetic Variables

Plasma concentrations for ribavirin, ritonavir, ABT-450, ABT-267 and possible metabolites of ABT-450 or ABT-267, and serum concentrations for pegIFN will be summarized.

5.4 Removal of Subjects from Therapy or Assessment

5.4.1 Discontinuation of Individual Subjects

Each subject has the right to withdraw from the study at any time. In addition, the investigator may discontinue a subject from the study at any time if the investigator considers it necessary for any reason, including the occurrence of an adverse event or noncompliance with the protocol.

If, during the course of study drug administration, the subject prematurely discontinues during the Substudy 1 Treatment Intensification Period, the procedures outlined for the Treatment Intensification Discontinuation (TI D/C) Visit should be completed as defined in [Table 5](#). Ideally, this should occur no later than 2 days after their final dose of study drug, and prior to the initiation of any other anti-HCV therapy. However, these procedures should not interfere with the initiation of any new treatments or therapeutic modalities that the investigator feels are necessary to treat the subject's condition. The dosing end dates for each DAA and ritonavir and reason for discontinuation from Substudy 1 will be recorded in the eCRF.

The subject should continue to Substudy 2, the pegIFN/RBV Treatment Period, unless the investigator considers continued pegIFN and RBV inappropriate due to either intolerance or inadequate virologic response. If the subject prematurely discontinues during Substudy 2, the subject should return for PR D/C visit procedures as defined in [Table 5](#) and proceed to Substudy 3. If the investigator does not consider the subject appropriate to participate in Substudy 2, the subject should start Substudy 3, the Post-treatment Period for monitoring of HCV resistance and viral response. Following discontinuation of study drug, the subject will be treated in accordance with the investigator's best clinical judgment. The dosing end dates for RBV and pegIFN and reason for discontinuation from Substudy 2 will be recorded in the eCRF.

If a subject discontinues from the Post-treatment Period, the subject should return for post-treatment discontinuation procedures (PT D/C) as defined in [Table 7](#). The reason for discontinuation from Substudy 3 will be recorded in the Study Completion eCRF.

If a subject is discontinued prematurely with an ongoing adverse event or an unresolved laboratory result that is significantly outside of the reference range, the investigator will attempt to provide follow-up until a satisfactory clinical resolution of the laboratory result or adverse event is achieved.

In the event that a positive result is obtained on a pregnancy test for a subject or a subject reports becoming pregnant during the treatment period of the study, the administration of study drug (including RBV) to that subject must be discontinued immediately. Specific instructions regarding subject pregnancy can be found in Section 6.6. Subjects will continue to be monitored for antiviral drug resistance in the Post-Treatment Period as described in Section 5.1.4. The investigator is also encouraged to report the pregnancy information to the voluntary RBV Pregnancy Registry.

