This is an open-label, multiple-dose, rollover study exploring the safety, antiviral activity and pharmacokinetics of ABT-450 with ritonavir (ABT-450/r) + ABT-267 in combination with pegIFN and RBV in HCV genotype 1-infected subjects (including subjects with compensated cirrhosis) who have experienced virologic failure in a previous AbbVie/Abbott DAA combination study. Among subjects who previously experienced null or partial response to pegIFN/RBV treatment at any time prior to pre-screening for this study or any prior failure with pegIFN/RBV plus telaprevir in the previous AbbVie/Abbott study, enrollment will be limited to only those subjects in whom variants relative to appropriate prototypic reference sequence in HCV protease at positions 155, 156, or 168 or in HCV NS5A at positions 28, 29, 30, 31, 32, 58, or 93 are not present at the Pre-screening Visit. All other subjects will be allowed to enroll in Study M13-101 at the discretion of the investigator, regardless of whether variants at any of these amino acid positions are detected.

This protocol consists of three substudies. In Substudy 1, subjects who have experienced virologic failure in a previous AbbVie/Abbott DAA combination study may choose to enter this study and receive intensified treatment with ABT-450/r, ABT-267, pegIFN and RBV for 24 weeks. Subjects who complete or discontinue DAA treatment in Substudy 1 will enter Substudy 2. In Substudy 2, subjects receive pegIFN and RBV for an additional 24 weeks for a total treatment of up to 48 weeks across Substudies 1 and 2. In Substudy 3, subjects will be monitored for resistance and viral response for 48 weeks after discontinuation of study drug treatment.

Ongoing review of the data is planned in order to determine if a subject meets the virologic stopping criteria as defined in this protocol. Subjects who meet virologic stopping criteria during DAA treatment will discontinue ABT-450/r and ABT-267, but at the investigator's discretion may continue to receive pegIFN and RBV therapy for a total of 48 weeks across Substudies 1 and 2. Ongoing review of the data is also planned for non-efficacy (futility) assessment. Data will be assessed separately for the population of subjects who were null or partial responders to prior pegIFN/RBV or who had any prior failure to pegIFN/RBV plus telaprevir in the previous AbbVie/Abbott study, and for the population of subjects who do not fall in the previous population at the time of enrollment into this study.

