| QTcF | QTc using Fridericia's correction formula |
| RBC | Red blood cells |

| | |
|-------------------|---|
| RBV | Ribavirin |
| RNA | Ribonucleic acid |
| RVR | Rapid virologic response |
| SAE | Serious adverse event |
| SAS | Statistical Analysis System |
| SDP | Study Designated Physician |
| SDS | Sodium dodecyl sulfate |
| SC | Subcutaneous |
| SGOT | Serum glutamic-oxaloacetic transaminase |
| SGPT | Serum glutamic-pyruvic transaminase |
| SOC | Standard of care |
| SUSAR | Suspected unexpected serious adverse reaction |
| SVR | Sustained virologic response |
| SVR ₁₂ | Sustained virologic response 12 weeks post-dosing |
| SVR ₂₄ | Sustained virologic response 24 weeks post-dosing |
| TI | Treatment intensification |
| TSH | Thyroid stimulating hormone |
| ULN | Upper limit of normal |
| WBC | White blood cells |

Definition of Terms

| | |
|----------------------------------|--|
| Post-Treatment Period | 48 weeks duration after the last dose of study drug in Substudy 1 or 2 |
| Substudy 1 Study Drug | ABT-450/r, ABT-267, pegIFN, RBV |
| Substudy 2 Study Drug | pegIFN, RBV |
| Study Day 1 | First day a subject took study drug in Substudy 1 |
| Treatment Intensification Period | Substudy 1 |
| Treatment Period | Day 1 through last treatment visit in Substudy 1 or 2 |

| | | |
|------------|--|-----------|
| 2.0 | Table of Contents | |
| 1.0 | Title Page | 1 |
| 1.1 | Protocol Amendment: Summary of Changes | 2 |
| 1.2 | Synopsis | 4 |
| 1.3 | List of Abbreviations and Definition of Terms..... | 9 |
| 2.0 | Table of Contents | 12 |
| 3.0 | Introduction | 17 |
| 3.1 | Differences Statement..... | 29 |
| 3.2 | Benefits and Risks..... | 30 |
| 4.0 | Study Objective | 32 |
| 4.1 | Primary Objective | 32 |
| 4.2 | Secondary Objectives..... | 32 |
| 5.0 | Investigational Plan | 32 |
| 5.1 | Overall Study Design and Plan: Description | 32 |
| 5.1.1 | Pre-screening..... | 34 |
| 5.1.2 | Screening..... | 36 |
| 5.1.3 | Treatment Period (Substudy 1 and Substudy 2) | 38 |
| 5.1.4 | Post-Treatment Follow-Up Period (Substudy 3) | 40 |
| 5.2 | Selection of Study Population..... | 42 |
| 5.2.1 | Inclusion Criteria | 43 |
| 5.2.2 | Exclusion Criteria | 45 |
| 5.2.3 | Prior and Concomitant Therapy..... | 48 |
| 5.2.3.1 | Prior HCV Therapy..... | 49 |
| 5.2.3.2 | Prohibited Therapy..... | 50 |
| 5.2.3.3 | Post-Treatment Therapy..... | 51 |
| 5.3 | Efficacy, Pharmacokinetic, Pharmacogenetic, and Safety Assessments/Variables..... | 51 |

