Transient asymptomatic postbaseline serum ALT elevations of $> 5 \times$ ULN occurred at a frequency of 1% across active treatment arms and were evaluated by an external hepatic panel. The ALT elevations were asymptomatic, usually occurred within the first 4 weeks of treatment and typically declined with ongoing treatment. A disproportionate number of the cases were in women on concurrent systemic estrogen-containing therapy (i.e., contraceptives or hormone replacement) and discontinuation of the hormonal therapy with continuation or brief interruption of the DAA regimen led to resolution in serum ALT elevation. Concomitant use of systemic estrogen-containing medications is a risk factor for these postbaseline elevations in serum ALT. No ALT elevations $> 5 \times$ ULN were observed in subjects receiving progestins only or in subject receiving topical vaginal estrogen preparations. Among the cases of serum ALT elevation thought to be related to the DAA regimen, none resulted in hepatic dysfunction and they generally resolved or improved with ongoing treatment. All cases had resolved completely in the post-treatment follow-up.

ABT-450/ritonavir and ABT-267 (and its major inactive human metabolites) had no effects on embryo-fetal development in rodent and/or nonrodent species at maximal feasible exposures that provided AUC multiples at least 4-fold higher than exposure at the

recommended clinical doses. Clinical studies in women who are pregnant have not been conducted.

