Subjects who complete TI treatment will continue on to Substudy 2, the PR Treatment Period, for continued dosing of pegIFN and RBV. Subjects who prematurely discontinue TI treatment may also continue on to Substudy 2, unless the investigator feels it is not appropriate to continue pegIFN and RBV either due to toxicity or to lack of virologic response. Substudy 2 will begin the day after the last dose of DAA. Substudy 2 is designed to allow completion of pegIFN + RBV treatment for a total duration of 48 weeks across Substudies 1 and 2 and to monitor HCV RNA levels and emergence of any ABT-450 and ABT-267 resistance-associated variants.

For subjects who complete Substudy 1, an additional 24 weeks of pegIFN and RBV will be administered in Substudy 2. Subjects who complete 24 weeks of treatment in Substudy 2 should undergo the procedures listed in the PR Final/PR Discontinuation Visit in [Table 5](#) (and [Table 6](#) for cirrhotic subjects), not the PR Week 24 visit and then continue on to Substudy 3.

Subjects who receive less than 24 weeks of TI treatment in Substudy 1 may receive pegIFN and RBV in Substudy 2 at the discretion of the investigator, up to a total of 48 weeks across Substudies 1 and 2. All subjects will continue to return to the site on an outpatient basis for the PR Treatment study procedures identified in [Table 5](#) (and [Table 6](#) for cirrhotic subjects). For those subjects who do not complete 24 weeks of TI treatment in Substudy 1, additional study visits as indicated in [Table 5](#) (and [Table 6](#) for cirrhotic subjects) should be performed if required to complete a total of 48 weeks across Substudies 1 and 2. These additional visits are PR Week 24, PR Week 36 and PR

Final/PR Discontinuation Visit (which may be out to 48 weeks or earlier). All subjects should complete the PR Final/PR Discontinuation Visit procedures at that subject's final visit in Substudy 2. In some cases this final visit may fall in between study visits listed in [Table 5](#). Sites should ensure that subjects adhere to the study visits listed in [Table 5](#) (and [Table 6](#) for cirrhotic subjects). Subjects who cannot complete their study visit per the visit schedule should ensure they do not run out of study drug prior to their next study visit. Compliance is critical to ensure adequate drug exposure.

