6.6 Pregnancy

Subjects and their partners should avoid pregnancy and males should avoid sperm donation throughout the course of the study, starting with Study Day 1 and for 7 months (or per local RBV label) after the last dose of RBV.

Pregnancy in a study subject must be reported to AbbVie within 1 working day of the site becoming aware of the pregnancy. Subjects who report a positive pregnancy test during

the Treatment Period must be notified to stop RBV immediately. Administration of DAA's, including ritonavir, and Peginterferon may be continued at the investigator's discretion if the benefit of continuing therapy is felt to outweigh the risk (Section 5.4.1). Subjects will continue to be monitored for antiviral drug resistance in the Post-Treatment Period as described in Section 5.1.4.

Information regarding a pregnancy occurrence in a study subject and the outcome of the pregnancy will be collected for pregnancies occurring up to 7 months (or per local RBV label) after the last dose of RBV. The investigator is encouraged to report the pregnancy information to the voluntary RBV Pregnancy Registry as applicable.

Male subjects who are not surgically sterile must either abstain from sexual intercourse or agree to use a double barrier method of birth control (condom), including informing their partner(s) to use an effective method of birth control (e.g., contraceptive sponge, diaphragm, or vaginal ring with spermicidal jellies or creams) for 7 months (or per local RBV label) after the last dose of RBV. In the event of pregnancy occurring in the partner of an enrolled subject, the investigator should contact the AbbVie Study Designated Physician to discuss the potential benefit of the male subject remaining on study drug treatment. If considered appropriate, the subject may remain in the study and the investigator should counsel the subject on the pregnancy risks associated with RBV, and instruct him to use 2 effective forms of contraception (including at least one barrier method) for the remainder of the partner's pregnancy. The investigator is encouraged to report the partner's pregnancy information to the voluntary RBV Pregnancy Registry.

Pregnancy in a study subject is not considered an adverse event. However, the medical outcome of an elective or spontaneous abortion, stillbirth or congenital anomaly is considered a serious adverse event and must be reported to AbbVie within 24 hours of the site becoming aware of the event.

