Spontaneous Abortion Miscarriage experienced by study subject.

Elective Abortion Elective abortion performed on study subject.

Section 6.5 Adverse Event Reporting

Address following third paragraph previously read:

Has been changed to read:

Section 6.5 Adverse Event Reporting

Last paragraph previously read:

The sponsor will be responsible for Suspected Unexpected Serious Adverse Reactions (SUSAR) reporting for the Investigational Medicinal Product (IMP) in accordance with Directive 2001/20/EC. The reference document used for SUSAR reporting in the European Union (EU) countries will be the most current version of the Investigator's Brochure.

Has been changed to read:

In emergency situations involving study subjects when the primary Study Designated Physician (SDP) is not available by phone, please contact the 24-hour AbbVie Medical Escalation Hotline where your call will be re-directed to a designated AbbVie SDP.

AbbVie will be responsible for Suspected Unexpected Serious Adverse Reactions (SUSAR) reporting for the Investigational Medicinal Product (IMP) in accordance with

Directive 2001/20/EC. The reference document used for SUSAR reporting in the EU countries will be the most current version of the Investigator's Brochure.

Section 6.6 Pregnancy

Second paragraph, second sentence previously read:

Subjects who report a positive pregnancy test during the treatment period must be notified to stop all study medication (Section 5.4.1).

Has been changed to read:

Subjects who report a positive pregnancy test during the Treatment Period must be notified to stop RBV immediately. Administration of DAA's, including ritonavir, and Peginterferon may be continued at the investigator's discretion if the benefit of continuing therapy is felt to outweigh the risk (Section 5.4.1).

Section 6.7 Toxicity Management

First paragraph, last sentence previously read:

This table should be used in determination of the appropriate toxicity management as discussed in Section 6.7.1 and Section 6.7.2.

Has been changed to read:

This table should be used in determination of the appropriate toxicity management as discussed in Section 6.7.1 through Section 6.7.5.

Section 7.0 Protocol Deviations
"Alternate Contact:" previously read:

Alternate Contact:

Has been changed to read:

Alternate Contact:

Section 8.0 Statistical Methods and Determination of Sample Size
First paragraph previously read:

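### Protocol 5.4.1 and 6.6 give different stopping orders in pregnancy, and the stop-all rules in 5.4.1.1 at TI Weeks 12 and 24 conflict with the Synopsis and 5.1.3

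*Protocol*

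**What the plan says.** **Pregnancy.** Protocol 5.4.1 states that, on a positive test or a reported pregnancy during treatment, "the administration of study drug (including RBV) to that subject must be discontinued immediately". Section 1.3 lists Substudy 1 study drug as "ABT-450/r, ABT-267, pegIFN, RBV". Section 5.4.1 then adds: "Specific instructions regarding subject pregnancy can be found in Section 6.6". Section 6.6 has the subject stop RBV at once. For the other drugs it is permissive: the sentence names the DAAs and ritonavir first and goes on "and Peginterferon may be continued at the investigator's discretion if the benefit of continuing therapy is felt to outweigh the risk (Section 5.4.1", ending at a cross-reference back to 5.4.1.

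**Virologic failure.** Protocol 5.4.1.1 attaches an action to each of five criteria:

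- TI Week 4, HCV RNA not below 1,000 IU/mL: stop the DAAs; pegIFN/RBV at the investigator's discretion.
- TI Week 12, less than a 2 log10 fall from baseline: stop everything.
- TI Week 24, HCV RNA of 25 IU/mL or more: stop everything.
- Confirmed rise of more than 1 log10 from nadir: stop everything.
- Confirmed breakthrough or relapse: stop everything, if still on drug.

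A closing paragraph, which opens by naming the last two criteria, allows continued treatment if the sponsor's Study Designated Physician approves.

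The Synopsis covers subjects who, while on DAAs, meet the stopping criteria. Of these it says that they "will discontinue ABT-450/r and ABT-267, but at the investigator's discretion may continue to receive pegIFN and RBV therapy for a total of 48 weeks". Section 5.1.3 says: "Subjects who complete TI treatment will continue on to Substudy 2, the PR Treatment Period, for continued dosing of pegIFN and RBV". For subjects who leave TI treatment early, 5.1.3 permits Substudy 2 and 5.4.1 makes it the default. Both let the investigator decline because of poor tolerability or poor virologic response.

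**The concern.** These are dosing instructions, and two sites following different sections would treat the same patient differently.

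In pregnancy, what is at stake is continued exposure to the DAAs, ritonavir and pegIFN. The Introduction reports no embryo-fetal effects of ABT-450/ritonavir or ABT-267 in animals, but also says "Clinical studies in women who are pregnant have not been" conducted. That paragraph does not address pegIFN. Whether to continue is therefore a real medical judgement, and the protocol should state one rule for it.

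In virologic failure, the choice is between stopping and a further long course of pegIFN/RBV, whose toxicity Protocol 3.2 describes, in someone who has already failed.

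The choice also reaches the data. SVR12 and SVR24 are timed from the last actual dose of any study drug, and SAP 6.1 counts study drug end days from the last pegIFN injection plus 7 days. The section a site follows therefore shifts the last-dose date, the pegIFN/RBV exposure and the start of Substudy 3. It does not change whether the subject counts as having met a stopping criterion in the futility review.

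**Working it through.** There is no planned figure to reproduce. The check sets the current texts side by side and asks whether a site can obey both.

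| Situation | One section | Another section | Can both be obeyed? |
|---|---|---|---|
| Positive pregnancy test | 5.4.1: study drug must stop | 6.6: RBV must stop; the rest is discretionary | Only by stopping everything |
| Less than 2 log10 fall at TI Week 12 | 5.4.1.1: stop everything | Synopsis: stop DAAs; pegIFN/RBV may continue | Only by stopping everything |
| HCV RNA of 25 IU/mL or more at TI Week 24, TI course completed | 5.4.1.1: stop everything | 5.1.3: goes on to pegIFN/RBV | No |

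**Step 1, pregnancy.** The definition in 1.3 covers all four components, and the words in brackets in 5.4.1 show that more than RBV is meant. RBV stops under both sections. For the other drugs, 5.4.1 is mandatory and 6.6 is permissive. Each section cites the other and neither states precedence, so an investigator who uses the 6.6 discretion contravenes 5.4.1.

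**Step 2, TI Week 12.** The Synopsis addresses exactly the subjects who meet stopping criteria on DAAs and does not distinguish between criteria. Its action matches the Week 4 rule in 5.4.1.1, not the Week 12 rule. If pegIFN/RBV runs to the 48-week total, the difference is at most 48 - 12 = 36 weeks.

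**Step 3, TI Week 24.** The 5.1.3 sentence on completers has no exception for a subject with quantifiable HCV RNA at that visit. One section tells this subject to stop and another to go on. The difference is at most 48 - 24 = 24 weeks.

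**Step 4, early discontinuers.** A Week 12 failure who comes off the DAAs also falls under the early-discontinuer text of 5.1.3 and 5.4.1. Both let the investigator stop for poor virologic response, so stopping satisfies every section. The conflict is soft: these texts leave to judgement what 5.4.1.1 makes mandatory. They do not reach a subject who has completed 24 weeks of TI treatment.

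**Likely origin of the pregnancy conflict.** Appendix D shows that the superseded 6.6 wording was "must be notified to stop all study medication (Section 5.4.1", which agreed with 5.4.1. The change list has no entry for the 5.4.1 sentence. This explains the mismatch; the error itself lies in the two current sections.

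**The case against.** The best defence is that the specific provision governs the general one. Section 5.4.1 sends the reader to 6.6 for pregnancy, and the Synopsis speaks of stopping criteria as the protocol defines them, which leads to 5.4.1.1. An investigator who stops everything complies in pregnancy and at Week 12. This is a fair account of intent, and it stands as such. It does not make the order in 5.4.1 conditional, and it leaves the Week 24 completer with two opposite instructions.

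A second defence is that the sponsor-physician route in 5.4.1.1 might extend to Weeks 12 and 24, because its second sentence does not repeat the restriction to the last two criteria. The narrower reading is likelier, since the paragraph opens with that restriction, but the wider one cannot be excluded.

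Two stronger readings are tempting and are not supported:

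- A reader might infer that the Synopsis, 5.1.3 and 5.4.1 all flatly contradict 5.4.1.1 at both weeks. They do not. The early-discontinuer text allows for poor virologic response and does not reach a subject who completes TI treatment. The Synopsis sentence fits Week 24 poorly because the DAA course is then ending. The completer sentence has no bearing on Week 12.
- A reader might try to bound the Week 12 group by baseline viral load, arguing that high-baseline failures would also meet the rise-from-nadir criterion. That ignores the breakthrough criterion, which applies at any baseline once HCV RNA has been below LLOQ. In addition, meeting a second criterion does not remove the unqualified Week 12 stop.

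**Conclusion.** Both conflicts are in the current protocol and should be fixed. In pregnancy the conflict is confined to the DAAs, ritonavir and pegIFN; RBV is not in question, and 6.6 is probably meant to govern. In virologic failure the main conflicts are the Synopsis against the Week 12 rule (up to 36 further weeks of pegIFN/RBV) and the 5.1.3 completer sentence against the Week 24 rule (up to 24 further weeks). Section 5.4.1.1 is probably meant to govern there, but the text does not say so.

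The week counts are ceilings. They assume that treatment runs to the 48-week total and, at Week 12, that the investigator elects to continue. The conclusion also assumes the likelier reading of the sponsor-physician route, and that a subject who has taken the full 24-week TI course counts as having completed it even if the Week 24 value is quantifiable. The documents do not allow the number of affected subjects to be derived; planned enrollment is up to 35.

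**What to change.** 1. Reword the pregnancy sentence in 5.4.1 to: *RBV must be stopped immediately; for DAAs, ritonavir and pegIFN follow Section 6.6.*
2. State in the Synopsis, 5.1.3 and 5.4.1 that the criterion-specific actions in 5.4.1.1 take precedence.
3. Add to the 5.1.3 completer sentence: *except subjects whom Section 5.4.1.1 requires to stop all study drugs.* The exception should not cover everyone who meets any 5.4.1.1 criterion, because that would remove the Week 4 discretion and bar subjects whose continuation the sponsor's physician has approved.

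The cost is a few sentences in an amendment and a letter to sites. No procedure, visit or data item is added.
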